8.4 Baseline Measures

The baseline value is the last assessment taken prior to the first dose of study medication. In general, baseline value is the assessment taken on study Day 1 before the administration of study medication. If a measurement on Day 1 is missing, the last assessment taken at the screening period prior to the first dose of study medication will be used.

8.5 Missing Measurements

8.5.1 *Imputation of Missing Data for Binary Variables*

This imputation is applicable for all binary variables (ACR20/50/70, DAS28-CRP <2.6, DAS28-ESR <2.6, and remission status defined by CDAI, SDAI and Boolean definition).

If the response cannot be assessed due to missing data or a subject's early discontinuation, the following conventions will be implemented in a sequence:

- Any subject who prematurely discontinues the trial during the double-blind period after receiving study medication will have data imputed as non-responder at all scheduled protocol visits subsequent to the point of discontinuation up to the end of the double-blind period.
- After any imputation above or none, if for some reason the binary variable still can't be determined, including the case where baseline data is missing, then its value will be set to non-responder.

For listings, missing responses will be presented as missing.

8.5.2 *Imputation of Missing Data for Continuous Variables*

For the analysis of changes from baseline values (e.g., individual components of ACR, DAS28-CRP, and DAS28-ESR etc), missing values will be dealt with via the longitudinal repeated measures analysis assuming MAR (missingness at random).

For all safety (including laboratory measurements), and PK measures, missing values will not be imputed.

8.6 Missing, Unknown or Partial Dates

The BMS safety guidelines for conventions relating to the handling of missing or partial dates and the determination of appropriate default values in such cases (in particular, for concomitant medication dose start-dates and end-dates and AE onset dates) will be utilized.

8.7 Day Ranges for Analysis of Time Points

Subjects who do not always adhere strictly to the visit schedule timing in the protocol. Therefore the designation of visits during the double-blind period of the study will be based on the day of

evaluation relative to the trial (day of first study medication = study Day 1) rather than the nominal visit recorded in the eCRF. Mutually exclusive relative day windows are defined below to provide derived visits that correspond to the post-baseline time points. If a visit falls outside of the pre-specified visit windows, then the data collected at that visit will not be assigned a derived visit but will remain in the derived data sets. Determination of baseline values is addressed in [Section 8.2](#).

If a subject has more than 1 visit where a measurement is recorded within a window, the measurement closest to the target day will be used. In case of 2 visits being equidistant from the target, the earlier measurement will be used in analyses. For these safety indicators, the least favorable value (toward a positive response) in the window will be used.

Designation of visits for efficacy assessments, and other measures during the double-blind period is tabulated below.

Table 4: Days Ranges for Assessments at Every Scheduled Visits During the Double-blind Period

Visit	Target Day	ACR20/50/70,DA S28-CRP, DAS28- ESR, HAQ	MRI	Fatigue, SF- 36, Stiffness, BRAF-MDQ	Biomarker
Baseline /Day 1	1	1	1	1	1
D15	15	8-21		8-21	
D29	29	22-43	15-57	22-43	
D57	57	44-71		44-71	
D85	85	72-99	58-113	43-113	72-99

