Subjects who discontinue at any time during the Treatment Period must complete the Early Termination (ET) Visit assessments							
Procedure	Day 1	Wk 2 (approx. D 15)	Wk 4 (approx. D 28)	Wk 8 (approx. D 56)	Wk 12 or ET (approx. D 84)	30 day FU Visit (approx. Day 114)	Notes
Safety Assessments							
Physical Exam	X				X	X	
Height and Weight	X				X	X	
ECG	X		X		X	X	Not required if early termination (ET) visit
Vital Signs	X	X	X	X	X	X	See Section 5.3.1 for details
Adverse Events Assessment	X	X	X	X	X	X	
Laboratory Assessments							
Hematology (CBC with differential)	X	X	X	X	X	X	
Chemistry panel	X	X	X	X	X	X	Must include liver function testing; see Section 5.3.5 for details. For double-blinded period, fasting glucose is required.
Estimated Glomerular Filtration Rate (eGFR) - AUDIT	X	X	X	X	X	X	As performed by Modification of Diet in Renal Disease (MDRD) Study equation
Fasting lipid panel	X			X	X	X	At least 10 hour fasting prior to collection of sample
IgM, IgA, and IgG	X		X		X	X	
Urinalysis	X				X	X	
Rheumatoid Factor	X				X	X	
Anti-CCP2	X		X		X	X	

Table 5.1-2: Flow Chart for Protocol IM006016 - Double-Blinded Treatment Period^a							
Subjects who discontinue at any time during the Treatment Period must complete the Early Termination (ET) Visit assessments							
Procedure	Day 1	Wk 2 (approx. D 15)	Wk 4 (approx. D 28)	Wk 8 (approx. D 56)	Wk 12 or ET (approx. D 84)	30 day FU Visit (approx. Day 114)	Notes
ANA	X				X	X	
Anti- Ro (SS-A) and Anti-La (SS-B)	X				X	X	
Urine pregnancy test	X		X	X	X	X	WOCBP only; results confirmed prior to administration of study drug. See Section 3.3.3
ESR (performed locally)	X	X	X	X	X	X	Performed locally. Every effort should be made to ensure the person analyzing the ESR results is not involved in the efficacy assessments (see Section 5.4)
hsCRP	X	X	X	X	X	X	
Pharmacokinetics	X	X	X	X	X		See Section 5.5.1 for details
Efficacy Assessments							
Tender (68)/ Swollen (66) Joint Count	X	X	X	X	X	X	Must have at least 6 swollen/tender joints prior to randomization
Subject Assessment of Pain	X	X	X	X	X	X	QoL assessments; see Section 5.8
Subject's Global Assessment of Disease Activity	X	X	X	X	X	X	
Physician's Global Assessment of Disease Activity	X	X	X	X	X	X	
Physical Function (HAQ-DI)	X	X	X	X	X	X	
Fatigue (VAS)	X				X	X	
SF-36	X				X	X	

Table 5.1-2: Flow Chart for Protocol IM006016 - Double-Blinded Treatment Period^a							

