7.4 Extent of Exposure

7.4.1 Study Therapy

In general, extent of exposure will be summarized for the As-treated analysis population in two ways:

- by the number of study drug doses. Frequency distribution of number of doses will be summarized
- by the number of days the subject is known to be on study drug, ignoring any dosing interruptions

In general, exposure to study drug during the double-blind (DB) period in days is calculated as:

For subjects who discontinue study medication,

- Exposure = (date of last DB dose - date of first DB dose + 1) + 30.

The offset of 30 days represents 30 days of follow-up after last dose and is a lot longer than 5 times of half-life of the study medication. The frequency will be presented according to the duration ranges (in days) : <28, 29-56, 57-84 and so on.

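### SAP Table 4: the questionnaire Week 12 window overlaps two earlier windows despite being called mutually exclusive, and no rule keeps off-drug follow-up values out of Week 12

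*SAP*

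**What the plan says.** SAP 8.7 assigns each record to a derived visit by study day, "rather than the nominal visit recorded in the eCRF". It states: "Mutually exclusive relative day windows are defined below to provide derived visits that correspond to the post-baseline time points". If several measurements fall within one window, "the measurement closest to the target day will be used", and the earlier one if they tie.

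Table 4 has four window columns: ACR/DAS28/HAQ; MRI; Fatigue/SF-36/Stiffness/BRAF-MDQ; and Biomarker. In that order, after the visit label and target day, its later rows read:

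- "D29 29 22-43 15-57 22-43"
- "D57 57 44-71 44-71" (no MRI or biomarker entry)
- "D85 85 72-99 58-113 43-113 72-99"

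Protocol Table 5.1-2 schedules the four questionnaires at Day 1, Week 12/ET and the follow-up visit only. That visit is headed "30 day FU Visit (approx. Day 114", and joint counts, global assessments, HAQ-DI, ESR and hsCRP are collected there too. SAP 6.1 runs the double-blind period to 30 days after the last dose. SAP 7.4.1 remarks that this 30-day offset "is a lot longer than 5 times of half-life of the study medication".

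**The concern.** Windows that share days do not define a single derived visit for a record. The closest-to-target rule chooses between measurements inside one window; it does not say which of two windows a single measurement belongs to. A programmer therefore cannot implement the questionnaire column as written without an unstated decision. The wide D85 window also lets a value taken halfway through the 84-day course stand as Week 12.

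The second issue is that nothing in SAP 8.7 separates on-drug from off-drug records. A follow-up visit after early stopping can fall on a study day inside D85. For the continuous DAS28 endpoints, which are listed secondary endpoints analysed with a mixed model (SAP 4.2, 7.5.2), whether Week 12 then holds an off-drug value, an ET value or nothing would depend on the day the subject stopped.

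**Working it through.** **1. Overlap within each column.** The SAP's statement implies zero shared days. Intersecting the windows day by day:

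| Column | Windows | Shared days |
|---|---|---|
| ACR/DAS28/HAQ | 8-21, 22-43, 44-71, 72-99 | 0 |
| MRI | 15-57, 58-113 | 0 |
| Questionnaires | 8-21, 22-43, 44-71, 43-113 | 29 |
| Biomarker | 72-99 | 0 |

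For the questionnaires, D57 and D85 share Days 44-71, which is 71 − 44 + 1 = 28 days. D29 and D85 share Day 43, which is 1 day. The total is 29.

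**2. Which questionnaire records are affected.** No questionnaire is scheduled at Week 2, 4 or 8, so records on Days 43-71 come mainly from ET visits, or from follow-up visits after very early stopping. Discontinuers complete the Week 12/ET assessments (Protocol 5.3). An ET visit on any of Days 43-84 lies in the D85 window. This needs no assumption about follow-up attendance.

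**3. Completers.** If the ±5-day tolerance in Protocol Table 5.1-2 also covers the follow-up visit (an assumption), it falls on Days 109-119. Days 109-113 are inside the questionnaire D85 window. A Week 12 value near Day 85 is closer to target, so the follow-up value is used only if the Week 12 value is missing. None of Days 109-119 falls in the DAS28/HAQ window.

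**4. Early terminators, DAS28 and HAQ.** Assume a follow-up 30 days after stopping. It lies in 72-99 when the stop day is between 72 − 30 = 42 and 99 − 30 = 69. Taking ET as the stop day:

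- Days 42-69: the ET value is outside D85, and the follow-up value becomes the D85 value.
- Days 70-71: neither value is in D85 (follow-up on Day 100 or 101).
- Days 72-84: the ET value is the D85 value.
- Before Day 42: neither value is in D85.

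If the follow-up may come 25 to 35 days after stopping, the stop days that can reach the window widen to 72 − 35 = 37 through 99 − 25 = 74. On Days 72-74 the ET value is in the window as well and is almost always the one chosen. If SAP 6.1 is read as excluding visits more than 30 days after the last dose, the lower limit returns to Day 42.

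**5. Early terminators, questionnaires.** With the same 30-day follow-up, the closest-to-target rule makes the follow-up the D85 value for ET on Days 13-69 (13 + 30 = 43, the first day of the window). For ET on Day 70 both values are 15 days from target (85 − 70 and 100 − 85), so the earlier one, ET, is used. ET values are used for Days 70-84.

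**6. Are these values off drug?** Protocol 3.3.1 puts five half-lives at about 3 days, and SAP 7.4.1 agrees that 30 days is much longer. That shows drug clearance. It does not show how much clinical effect remains.

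**The case against.** **Most of the table is sound.** Three of the four columns do not overlap, including the one used for the co-primary endpoints. A reader might infer that the primary analysis is affected. It is not: SAP 8.5.1 sets ACR20/50/70 and the binary remission endpoints to non-response after discontinuation. This stands.

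**The questionnaires carry little weight.** They are not among the listed primary or secondary endpoints, and Protocol 8.4.6 plans only descriptive summaries for Fatigue, Stiffness and BRAF-MDQ. A wide window is understandable for an instrument with one scheduled on-treatment visit after baseline. The 29 days are calendar days, and few records should fall on them. This stands as to size, but the table still contradicts its own description.

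**Follow-up attendance is not certain.** Protocol 5.3 names the 30-day visit only for subjects who complete the study. Protocol 3.5 to 3.6.1, however, require those who stop drug to continue with follow-up procedures. The off-drug part is therefore conditional.

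**Using off-drug values can be a legitimate choice.** Protocol 3.6 asks for outcome data after discontinuation. A reader might infer that these values invalidate the missing-at-random assumption in SAP 8.5.2. That does not follow, because an observed post-discontinuation value is not missing. What can be said is that the SAP does not state whether such values are meant to represent Week 12.

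**No dilution figure can be given.** A reader might want a percentage loss of the Week 12 effect. The documents give neither a stopping rate for Days 42-69 nor the effect remaining after 30 days off drug, so any figure would be invented.

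**Conclusion.** The point holds in limited form and is minor. The questionnaire column of Table 4 contradicts the SAP's own description on 29 study days, and ET questionnaires from Day 43 onward can be labelled Week 12. Both follow directly from the table and the visit schedule.

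The off-drug part is conditional. If discontinuers attend a follow-up about 30 days after stopping, stop days of about 42-69 place an off-drug value in D85 for continuous DAS28 and HAQ. CDAI and SDAI are exposed in the same way only if that column's windows are meant for them, since Table 4 does not name them. Completers with a Week 12 value and all binary endpoints are protected. The wording should remain that such values can be reported as Week 12; the documents do not show that they will be, or how often.

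**What to change.** Make three edits to SAP 8.7:

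1. Set the D85 window for Fatigue, SF-36, Stiffness and BRAF-MDQ to 72-99, as for ACR/DAS28. Shared days fall from 29 to 0.
2. Delete the D15, D29 and D57 entries in that column, which match no scheduled questionnaire visit, or keep them only to hold ET values.
3. Add that the 30-day post-treatment follow-up visit is not assigned to D85 in the Week 12 efficacy and questionnaire summaries. The first edit does not achieve this alone, because stopping on Days 42-69 still gives a follow-up on Days 72-99. Say also that ET values on Days 72-84 remain eligible for D85.

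Deleting the earlier rows while keeping 43-113 would remove the overlap but would still count half-course ET values as Week 12.

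The cost is a table edit and a sentence or two before database lock. Subjects who terminate before Day 72 would contribute no Week 12 questionnaire value, and no post-baseline questionnaire value at all if the earlier rows are deleted. A few follow-up values would leave the Week 12 continuous analyses.

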9 CONTENT OF REPORTS

The results of the study conducted by Protocol IM006-016 will be presented in a standard BMS CSR appendix. Key results and any unanticipated findings that are unusual for this study will be identified. A meeting for the initial dissemination of study results will be held after database locked. Attendees at this meeting will review all efficacy and safety summaries and listings and will identify key results that should be highlighted in the CSR.

1.0		12/04/2015	Original version
-----	--	------------	------------------
